We propose a pilot study to assess the feasibility of enrolling ~50 community-dwelling, ambulatory women aged 65 years and older with urgency or mixed urgency predominate urinary incontinence into a randomized, controlled trial, to determine whether elderly women will adhere to an 8-week drug regimen and estimate the effect size necessary to show differences cognitive decline between Mirabegron and a standard anticholinergic therapy.

B. STUDY SYNOPSIS

Fifty community-dwelling women, ambulatory women with urgency or mixed urgency predominate urinary incontinence and at least 3 urgency incontinence episodes on a 3-day ~~screening diary, will be randomized to 8 weeks of Mirabegron (Myrbetriq) or tolterodine~~

tartrate (Detrol LA). The study will take place at the UCSF Women's Health Clinical Research Center.

C. SPECIFIC AIMS

The Specific Aims are to:

SA1: Assess the feasibility of enrolling and retaining women aged 65 years and older with urgency urinary incontinence in a randomized, controlled trial of an 8-week medication study.

SA2: To estimate preliminary differences in the effects of mirabegron compared to a standard anticholinergic therapy on cognitive function and calculate the standard deviation for: 1) a standard cognitive function battery, and 2) global patient perception of cognitive function.

SA3: To collect preliminary data on differences in change in physical function/mobility and other adverse events associated with Mirabegron vs. a standard anticholinergic therapy, such as dry mouth, constipation, vision, and falling.

SA4: Determine the differences in patient satisfaction between Mirabegron and a standard anticholinergic therapy in the treatment of urgency urinary incontinence.

SA5: To estimate preliminary differences in the efficacy of Mirabegron compared to a standard anticholinergic therapy on reducing urinary incontinence frequency, as assessed by validated 3-day voiding diary.

D. STUDY POPULATION

D1. Inclusion Criteria

Inclusion criteria reflect patients appropriate for treatment by primary care.

- Community-dwelling, ambulatory females \geq 65 years old

- Urgency or Mixed Urgency Predominate Urinary Incontinence (subject-reported) for ≥ 3 months prior to Screening (Visit 1)
- On a 3-day voiding diary, documentation of at least 3 urgency incontinence episodes with the number of urgency incontinence episodes greater than number of stress incontinence episodes

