The daily voiding diary period is defined as follows: "Awake Time" begins from the time the subject starts her day (time arose) until she goes to bed for that day. "Bed Time" is defined as the time the subject went to bed until she awoke to start the next day.

E5. Evaluation Schedule

Time of Visit	Tele-phone	SV	Base line	2wk phone	4wk	8wk	ET
Telephone Screening	X						
Information & Informed Consent		X					
3-day voiding diary Instruction		X					
Demographics		X					
Alcohol and Tobacco Use		X					
Medical History		X					
Mini-Mental Status Exam (MMSE)*		X					
Geriatric Depression Scale (GDS)*		X					
Concomitant Medication		X					
Dipstick urinalysis		X				X	X
PVR assessment		X				X	X
Voiding diary Review			X		X	X	X
Height^ and Weight			X			X	
Vital Signs		X	X		X	X	X
Health and Medications Update			X	X	X	X	X
Inclusion/Exclusion/Randomization			X				
Dispense study medication			X		X		
California Verbal Learning Test – Short Form (CVLT-SF)			X			X	X
Digit Span			X			X	X
Trail Making Test Parts A & B			X			X	X
Digit Symbol Substitution Task (DSST)			X			X	X
Pittsburgh sleep quality index (PSQI)			X			X	X
Epworth Sleepiness Scale (ESS)			X			X	X
Physical Function and Mobility: Short Physical Performance Battery (SPPB)			X			X	X
IADL			X			X	X
OAB-questionnaire			X			X	X
Patient Perception of Cognitive Change				X	X	X	X
Adverse events (self-report)				X	X	X	X

Patient Perception of Bladder Condition				X	X	X	X
Participant directed Dose Adjustment				X	X		
Assess study medication compliance				X	X	X	X
Trial medication return/count					X	X	X
Early Termination Report							X
Participant Satisfaction						X	X

[^] Height only at baseline visit

* The MMSE and the GDS will be used only as screening tests to determine eligibility, not as outcome measures

E6. Study Visits

The 8-week RCT requires 2 telephone visits (Telephone Screening, Week 2 Phone Call) and 4 in-clinic visits (Screening, Baseline, Week 4, Week 8 (or Early Termination) visit).

E6.1 Recruitment Phase

Women will be recruited by (1) direct, community-based efforts using large media (newspaper notices, television ads, etc.) and small media (brochures in local businesses, talks to local community, notices in churches, salons etc.); (2) seeking referrals from physician's offices (specifically in urology, urogynecology, gynecology, primary care, and geriatric medicine) and (3) purchasing targeted mailing lists.

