1.2 F3. Global Patient Perception of Cognitive Change

A single-item assessing patient's overall perception of their memory problems using a 5-point Likert scale, participants will be asked "Compared to 4 weeks ago, have you noticed that your memory and thinking are:" with responses of much better, somewhat better, about the same, somewhat worse, or much worse.

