1.5 F8. Global Rating of Patient Satisfaction and Perceptions of Improvement

Two validated questions assessing patient's satisfaction with the intervention and perception of improvement of their bladder problems will be administered: ³¹

- Patient satisfaction question (PSQ): How satisfied are you with your progress in this program? With responses of Completely, Somewhat, or Not at all
- Global perception of improvement (GPI): Overall, do you feel that you are: Much Better, Better, About the same, Worse, or Much worse. This is compared to pre- intervention (so there is no baseline value).

F9. Other Measurements

Weight will be recorded in kilograms using a calibrated scale. Participants will be measured in light clothing (without shoes) to the nearest 0.5 kg. Standing height, which is measured at the baseline visit only, will be measured in centimeters with a calibrated wall-mounted Harpenden

stadiometer or ruler. Variables that may act as predictors of the frequency of incontinence will be documented at screening or baseline. These covariates include demographic characteristics (age, race/ethnicity, residency location (independent, assisted), relationship status, education), general health, genitourinary history (duration of incontinence, prior type and duration of therapy, amount of urine loss, pad use, drinking habits), smoking behavior, reproductive health (gravity, parity, route of delivery, menopause status, hormone therapy use), medical history/comorbidities (hypertension, cardiovascular disease, pulmonary disease, stroke, diabetes) surgical history (hysterectomy, pelvic organ prolapse repair, other pelvic or abdominal surgery), history of falling on past month, and medications.

G. DATA MANAGEMENT

G1. Data Collection

A secure study database will be developed using the UCSF Research Electronic Data Capture system (REDCap). REDCap enables researchers to create on-line databases for input, cleaning, management, and exporting of all study data. The study programmer analyst, who has previously used REDCap to create study databases for large multi-centered studies, will create a REDCap database unique to our study. REDCap also contains advanced features for data cleaning, importing, and embedded calculated database fields and is supported by the UCSF Information Technology Service.

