SA 3: Standard chi-square tests will be used to determine differences in report of adverse events at week 8.

SA 4: Number and proportion of participants reporting much better, somewhat better, about the same, somewhat worse and much worse memory and thinking since study enrollment will be calculated. Chi-square test for trend will be used to determine differences patient perception of cognitive change at week 8.

SA 5: ANCOVA will be used to estimate the preliminary differences and calculate the standard deviation of change in incontinence episode frequency measured on the 3-day diary between the Mirabegron and standard anticholinergic therapy groups at week 8, controlling for baseline.

M. NONADHERENCE, STUDY DRUG DISCONTINUATION AND EARLY STUDY DISCONTINUATION

All participants will be encouraged to take all doses of study medication unless safety is a concern. Study coordinators will ascertain reasons for nonadherence to study medication and attempt to help participants find ways to improve adherence. However, participants who are nonadherent with study medication will be urged to attend all study visits and complete all study measurements as planned. Adherence with study medication will be measured by tablet counts at each clinic visit.

Study drug will be discontinued in any participant who has any serious adverse event that, in the judgment of the clinical site investigator, is possibly related to treatment with study medication. Study medication may be resumed if, in the opinion of the clinical site investigator, the abnormal symptom, physical finding or test has been satisfactorily evaluated and found to be benign.

Participants will be considered to have permanently discontinued study medication if they report not taking study medication for 4 weeks or longer. In this case, study termination measurements will be obtained if possible.

All participants will be urged to attend all study visits and complete all study measurements as planned. However, participants can discontinue participation in the study at any time. Participants who miss a visit will be contacted by the study coordinator to reschedule the visit and to provide assistance in completing the visit. Participants who state that they no longer desire to participate in the trial will undergo study termination measurements if possible.

N. REFERENCES

1. Mitteness LS. The management of urinary incontinence by community-living elderly. *Gerontologist* 1987;27:185-93.

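### Section L's SA 4 paragraph analyses the memory-perception item instead of patient satisfaction, and reports a four-week comparison as change since enrolment

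*Combined protocol and SAP*

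**What the plan says.** Section C (Specific Aims) gives the fourth aim as "SA4: Determine the differences in patient satisfaction between Mirabegron and a standard anticholinergic therapy". The second aim undertakes to estimate arm differences and to "calculate the standard deviation for: 1) a standard cognitive function battery, and 2) global patient perception of cognitive function". Self-perceived cognition is therefore an SA2 outcome.

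Three instruments in section F matter here:

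- **F8, patient satisfaction question (PSQ):** "With responses of Completely, Somewhat, or Not at all".
- **F8, global perception of improvement (GPI),** presented alongside the PSQ: "Much Better, Better, About the same, Worse, or Much worse".
- **F3, perception of cognitive change:** the question put to the participant is "Compared to 4 weeks ago, have you noticed that your memory and thinking are". It is answered on a five-level scale, which F3 sets out as follows: "with responses of much better, somewhat better, about the same, somewhat worse, or much worse".

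The E5 schedule has a row "Participant Satisfaction" marked at Week 8 and early termination (ET). Perception of cognitive change is marked at Weeks 2, 4 and 8 and at ET, with no baseline administration.

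Under SA 4, section L plans to calculate "Number and proportion of participants reporting much better, somewhat better, about the same, somewhat worse and much worse memory and thinking since study enrollment", and then to apply a chi-square test for trend to perceived cognitive change at week 8.

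**The concern.** An analyst who follows L will report a memory result under SA4 and no satisfaction result. The summary measure and the test for a stated aim would then be chosen without a plan, possibly after the arm-level data are known.

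The second problem is one of meaning. L presents the memory answers as change since enrolment, but the question put to participants refers to four weeks earlier. By Week 8 that reference point lies inside the treatment period. A woman who noticed worsening in the first month and no further change could truthfully answer that she is about the same. L would describe her as unchanged since she entered the study. Cognitive effect is the question that motivates this pilot, so the description of this result matters.

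**Working it through.** The plan gives no figure to reproduce on this point, and section K says that no power analysis was done. The check sets the sections side by side.

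**Step 1. Does any paragraph of L analyse satisfaction?**

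| Paragraph in L | What it analyses |
|---|---|
| SA 1 | Recruitment, retention, discontinuation, recruitment cost |
| SA 2 | Cognitive test scores; physical function and mobility scores |
| SA 3 | Adverse events |
| SA 4 | Perceived memory and thinking |
| SA 5 | Incontinence episode frequency |

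None does: the count is zero of five.

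**Step 2. Could the SA 4 paragraph be loose wording for satisfaction?** The number and wording of the response levels decide this.

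- The PSQ has three levels and none of them matches L.
- The GPI has five levels, but its second and fourth are plain better and worse.
- The F3 item has five levels, with the second and fourth qualified by somewhat, exactly as in L.

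L also names perceived cognitive change as what is tested. The paragraph is an analysis of the F3 item.

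**Step 3. Does the paragraph deliver what SA2 promises for that item?** SA2 promises a standard deviation. L gives counts, proportions and a trend test. The SA 2 ANCOVA does not supply the SD either: it is limited to test scores and controls for baseline, and the item has no baseline value. The SD can, however, be recovered. Score the levels k = 1 to 5, let n_k be the count at level k in an arm and N the arm total. Then

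mean = Σ k·n_k / N, and SD = √[ Σ n_k·(k − mean)² / (N − 1) ].

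Both follow from the counts that L already reports once a scoring is stated.

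**Step 4. What does each answer compare with?** If visits are on schedule, an answer at treatment week t refers to week t − 4:

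| Answer given at | Reference point |
|---|---|
| Week 2 | 2 − 4 = −2, about two weeks before baseline |
| Week 4 | 4 − 4 = 0, about baseline |
| Week 8 | 8 − 4 = 4, on treatment |

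Only the Week 4 answer measures change from about the start of treatment. The SA 1 paragraph of L treats enrolment and randomisation as the same step, so change since enrolment means change since week 0. The Week 8 answer, to which L attaches its test, does not measure that.

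**The case against.** The strongest reply is that this is a drafting slip in a pilot. L's aim labels are loose elsewhere: physical function is named in SA3 in section C but is analysed under SA 2 in L. That explains how the error may have arisen but does not remove it. Physical function still receives an analysis, whereas moving the memory paragraph to its proper place leaves SA4 empty.

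Some stronger readings are tempting, and the documents do not support them.

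- **A reader might infer that the trial cannot see early cognitive change.** The memory item is also asked at Weeks 2 and 4, and L's tabulation sentence names no visit. The cognitive battery is compared at week 8 controlling for baseline, so it spans all eight weeks. Only the Week 8 self-report test misses a difference that arose early and then held.
- **A reader might treat the Week 2 answers as compromised because they look back before randomisation.** The item compares two points in time, and an untreated reference point is a legitimate one. The share of the look-back that falls before randomisation does not measure bias.
- **A reader might infer that the SD is lost.** It is not, as Step 3 shows. Section K, moreover, names only the neuropsychological battery SD as a goal. This is a wording gap.
- **A reader might assume that the gap can certainly be closed blind.** E6.4.a keeps the codes unbroken until lock but allows an exception by the Executive Committee. Section H has an unblinded biostatistician at the research center preparing reports for reviews after 20 and 40 participants complete the 4-week visit. Interim efficacy assessment is excluded, so the risk is modest. The documents do not show whether lock has already passed.

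It is also true that L gives no rule for ET answers under any aim, so that omission adds no weight against SA 4 in particular.

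**Conclusion.** Wrong as written, and worth correcting. One of the five stated aims has no analysis in L. The paragraph bearing its number analyses an SA2 outcome and describes a four-week comparison as change since enrolment. At Week 8 that comparison is with on-treatment week 4.

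The consequence is limited. Satisfaction is defined and scheduled, so no data are lost. The memory analysis is usable once it is refiled and correctly described, and other planned measures cover the early weeks. The plan makes no power claim that could be affected.

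The conclusion assumes that visits occur on schedule and that enrolment means randomisation, as L's SA 1 paragraph uses the term. The documents do not say whether SA4 is meant to include the GPI as well as the PSQ. Neither is analysed in L, so the conclusion does not depend on the answer.

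**What to change.** Amend section L. The amendment should be written by staff who have not seen arm-level data, and should say so.

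1. **SA 4.** Report PSQ counts and proportions by arm, and a between-arm difference with a 95% confidence interval as a preliminary estimate. If the three levels are dichotomised, fix the cut in advance; where to place it is the sponsor's choice. Apply the chi-square test for trend that the paragraph already names. State whether the GPI is part of SA4 and, if so, how it is summarised.
2. **SA 2.** Move the memory-perception paragraph here. Keep the counts, proportions and trend test, and add the mean and SD by arm on a stated scoring, for example 1 for much better to 5 for much worse.
3. **Time frame.** Describe the memory answers as compared with four weeks ago. Report the Week 4 answer (change from about baseline) beside the Week 8 answer (change from week 4).
4. **Early termination.** State one rule and use it for both items. For example, count each randomised woman once in her assigned arm, by her Week 8 answer or, if she left early, her ET answer. Repeat with Week 8 answers only as a sensitivity analysis.

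The cost is two short paragraphs of L, a little extra analysis, and the ethics committee approval that section I1 requires for any amendment. Both items are already scheduled, so no visits, questions or participants are added.

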- Urinary retention (post-void residual urine volume >150 cc measured by bladder scan at screening).

[figure not shown]
- Use of any electrostimulation, bladder training, or pelvic floor exercises (with certified incontinence practitioners) within 4 weeks of Screening.
- Use of mirabegron or tolterodine in the past 6 months.
- Has been treated within 4 weeks prior to Screening and/or is currently being treated with:
 - Any drug treatment for OAB
 - Any drugs with significant anticholinergic and antispasmodic effects (see exception for tricyclic antidepressants below)
- Has started treatment with or changed dose of tricyclic antidepressants or estrogens within 4 weeks prior to Screening.
- Intermittent use or unstable dose of diuretics. Treatment with diuretics initiated within 4 weeks prior to baseline and/or is not on a stable dose is not permitted.
- Treatment with potent CYP3A4 inhibitors, such as clarithromycin, ketoconazole, and itraconazole within 4 weeks prior to Screening.
- Administration of medications capable of inducing hepatic enzyme metabolism or transport (e.g., barbiturates, rifampicin, carbamazepine, phenytoin, primidone, or St. John's Wort) in the past 4 weeks.
- Administration of narrow therapeutic index drugs metabolized by CYP2D6, such as thioridazine, flecainide, and propafenone.
- Previously received any investigational drug within 30 days prior to trial entry.
- Alcohol and/or any other drug abuse in the opinion of the investigator.
- Participants who, in the opinion of the Investigator, have any medical (including known history of major hematological, renal, cardiovascular, or hepatic abnormalities) or psychological condition or social circumstances that would impair their ability to participate reliably in the trial, or those who may increase the risk to themselves or others by participating.
- Participants who, in the opinion of the investigator, are not likely to complete the trial for whatever reason.

Participants must meet all inclusion and exclusion criteria to be randomized to trial treatment.

E. STUDY DESIGN

Approximately 50 women with urgency or mixed urgency predominate urinary incontinence will be randomized in a 1-to-1 ratio to either mirabegron or tolterodine tartrate for 8 weeks.

E1. Study Overview

E2. Study Medication and Placebo

E2.a Dosing Regimen

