Participants will be instructed to take one tablet and 1 capsule (total of 2) of blinded study medication once a day, orally, for 8 weeks. They will start with a Mirabegron (25mg) or tolterodine tartrate (4 mg) dose of study medication and will have the option of dose escalation to 2 tablets and 2 capsules (total of 4) per day (Mirabegron 50mg or tolterodine tartrate 4 mg + identical placebo).

- Mirabegron (25 mg or 2 X 25 mg) with participant-directed dose adjustment
- Detrol LA (4mg or 4mg + placebo) with participant-directed dose adjustment

E2.b Study Medication Supply

Mirabegron (Myrbetriq), tolterodine tartrate (Detrol LA) and placebo tablets identical to the tolterodine tartrate tablets administered in the study will be supplied by Astellas, shipped to the UCSF Pharmacy, and labeled by the pharmacist with randomization numbers. Because the two treatments cannot be made identical, the study will use a double-dummy methodology with the placebo identical to the tolterodine tartrate but these will not be identical to the Mirabegron. Specific procedures for shipping, storing, labeling, logging and returning study medication and for dispensing study medication to participants will be described in detail in the Operations Manual.

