1.1.1 E2.c Study Medication Accountability

Study Medication Accountability Forms and logs will be used to maintain accurate records of receipt, dispensing, return, and disposal of study medication. When drug is received, the

date, randomization number and quantity of drug received will be recorded. During the study, participants receiving study medication should be identified on the drug accountability form by study-specific participant number and acrostic. In addition, the date and quantity dispensed should be recorded each time study medication is dispensed.

All study medication receipts, dispensing, transfers, returns, and disposal of drug are to be documented on the study medication accountability form. Specific procedures for the drug accountability of study medication will be included in the Operations Manual.

E2.d Study Drug Disposal

All doses of study medication that remain undispensed at the end of the study should be properly disposed per UCSF Pharmacy guidelines. It is the responsibility of the Investigator or designee to determine investigational drug accountability, complete the record and ensure that the unused investigational drug is destroyed.

Specific procedures for study medication handling will be included in the Operations Manual.

E3. Titration Sequence

	Baseline (V1)		Phone Call Week 2 (V2)		Week 4 (V3)		Week 8 (V4)
1	Mirabegron 25mg	→	↑ Mirabegron 50mg if desired	→	Same or adjust Mirabegron	→	Final Data
2	Tolterodine tartrate 4mg	→	↑ tolterodine tartrate 4mg + Matching placebo if desired	→	Same or adjust tolterodine tartrate 4mg + Matching placebo	→	Final Data

E4. Evaluation criteria

Primary efficacy will be measured as change in the number of urge incontinent episodes per day from baseline to 8 weeks. A reliable and validated 3-day voiding diary will be used that includes frequency of micturitions (diurnal and nocturnal) and incontinence episodes classified by clinical type (urgency, stress, or other) along with time of occurrence, waking and bedtime.¹⁶⁻

¹⁸ Details recorded in diary:

- Time arose from and time went to bed
- Time of every micturition
- The participant will rate their degree of urgency with each micturition episode
- Time of every incontinence episode
- The participant will report the reason for the incontinence episode (urgency, stress, other)

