1.7 I1. Institutional Review Board

The study protocol, informed consent form, study questionnaires and recruitment materials must be approved by the UCSF Committee on Human Research (CHR) prior to the start of the study. Protocol amendments generated during the study must be approved by the CHR prior to their implementation. The Sponsor-Institution (UCSF) and Investigator ([name]) shall be

responsible for reporting any serious adverse events associated with the use of the study drug to the ASMA (e-mail [contact] or fax to [contact]) and to the UCSF CHR.

I2. Informed Consent Form

Before individuals may participate in any screening procedures, informed consent for all phases of the trial must be obtained. The consent form will explain in lay language the goals of the study, the visits and procedures and the risks and benefits of participating. Any amendment to the protocol generated during the study that impacts participants will be reflected in a revised consent form that must be signed again by the participant.

K. SAMPLE SIZE JUSTIFICATION

Sample sizes between 24 and 50 have been recommended for feasibility/pilot studies.³²⁻³⁵ We plan to study up to 50 women with approximately 25 randomized to Mirabegron and 25 to a standard anticholinergic therapy (Detrol LA). One of the goals of this study is to estimate the standard deviation of the neuropsychologic battery scores as well as the potential effect size of Mirabegron against its comparator. These estimates will be used to develop sample size estimates for a larger clinical trial, if indicated. Thus, power analyses based on a sample size of 50 were not done for this proposal.

L. STATISTICAL CONSIDERATIONS

SA 1: We will observe the number of weeks required to enroll 50 participants into this pilot study, track the success rate of various recruitment approaches, track the numbers of women who are screened, found eligible, enrolled/randomized, and lost to follow-up, as well as those to terminate the study or discontinue study medication early, and calculate the cost of recruitment per participant.

SA 2: Analysis of covariance (ANCOVA) will be used to estimate the preliminary performance differences on and calculate the standard deviation of cognitive test scores and physical function and mobility test scores between the Mirabegron and standard anticholinergic therapy groups at week 8, controlling for baseline.

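### Does the four-week rule for permanent drug discontinuation make the feasibility count miss women who stop in the second half of treatment?

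*Combined protocol and SAP*

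**What the plan says.** Section E states that about 50 women "will be randomized in a 1-to-1 ratio to either mirabegron or tolterodine tartrate for 8 weeks". The summary of the pilot lists among its purposes "to determine whether elderly women will adhere to an 8-week drug regimen".

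Section L, SA 1, is a list of things to track: enrolment time, recruitment yield, numbers screened, eligible, randomized and lost to follow-up, "as well as those to terminate the study or discontinue study medication early". It gives no definition of early and does not refer to Section M.

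Section M contains the only time-based rule: "Participants will be considered to have permanently discontinued study medication if they report not taking study medication for 4 weeks or longer". The next sentence gives the consequence, which is that termination measurements are obtained where possible. Section M also provides for stopping drug after a possibly related serious adverse event, with resumption allowed. On adherence it says "Adherence with study medication will be measured by tablet counts at each clinic visit".

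The schedule in E5 has a row headed "Assess study medication compliance", marked at the Week 2 call, Week 4, Week 8 and early termination. A return/count row is marked at Week 4, Week 8 and early termination. Section E2.c adds that "the date and quantity dispensed should be recorded each time study medication is dispensed".

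**The concern.** A rule that needs four weeks off drug sits awkwardly in an eight-week treatment period, because it can only recognise stops in the first half. Section M has drug discontinuation in its title and holds the only time criterion in the plan, so an analyst looking for a definition to use in SA 1 might take it from there. Stops in Weeks 5 to 8 would then drop out of the discontinuation count, while a colleague who read the word plainly would include them. The same data could give two different rates.

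Whether older women stay on the regimen is one of the questions the pilot exists to answer. With about 25 women per arm, moving a few of them shifts the estimate visibly. An undercount caused by a definition also runs in one direction and does not show in a confidence interval. In addition, Section L names no adherence summary, although drug counts are collected.

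**Working it through.** The plan states no discontinuation rate or dropout allowance, so there is no figure of its own to reproduce. The check has three parts.

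**1. What the rule can classify.** Inputs: treatment of 8 × 7 = 56 days (Section E); gap of 4 × 7 = 28 days (Section M). With last dose on day *s* and contact on day *V*, the rule is met if *V* − *s* ≥ 28.

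- Week 2 (*V* = 14): 14 − 28 = −14, so it cannot be met.
- Week 4 (*V* = 28): 28 − 28 = 0, so it is met only if nothing was taken after day 0.
- Week 8 (*V* = 56): 56 − 28 = 28, so it is met only if the last dose was on or before day 28. Last doses on days 29 to 55 leave 27 down to 1 days off drug.
- Week 8 visit 7 days late (assumed; no window is stated): 63 − 28 = day 35.

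The day-28 limit is therefore real.

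**2. How many stops would be missed if this rule defined the SA 1 count.** Let *q* be the share stopping by Week 8 (assumed 10% to 40%) and *r* the ratio of the hazard in Weeks 0–4 to that in Weeks 4–8 (assumed 0.5 to 3). Then P(stop by Week 4) = 1 − (1 − *q*)^(*r*/(*r*+1)), and the share missed is 1 − P/*q*.

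For *q* = 0.20 and *r* = 1: P = 1 − 0.80^0.5 = 0.106; share missed = 1 − 0.106/0.20 = 47.2%; of 50 × 0.20 = 10 stops, 4.7 are missed.

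| Hazard pattern | Share missed, *q* = 10% to 40% | Women missed of 10, *q* = 20% |
|---|---|---|
| Constant (*r* = 1) | 48.7% to 43.6% | 4.7 |
| Front-loaded (*r* = 2) | 32.2% to 27.8% | 3.1 |
| Front-loaded (*r* = 3) | 24.0% to 20.4% | 2.3 |
| Back-loaded (*r* = 0.5) | 65.5% to 60.9% | 6.4 |

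For scale, the exact 95% interval is 10.0% to 33.7% for 10/50 and 3.3% to 21.8% for 5/50. The two intervals overlap widely.

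These shares are upper bounds, because they treat every stop after day 28 as lost. SA 1 separately counts losses to follow-up and study terminations, and E5 schedules an Early Termination Report, so a woman who stops drug and leaves in Weeks 5 to 8 still appears in the attrition figures. A stop for a possibly related serious adverse event is a discontinuation under Section M whatever its length. Only women who stop late, stay in the study and have no such event could vanish.

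**3. Whether the rule does define the count, and whether late stops can be seen.** SA 1 speaks of stopping early; Section M defines permanent discontinuation and uses it to prompt measurements. These are different terms with different uses, and neither section cites the other. Read plainly, SA 1 counts any stop before Week 8, and the number missed is 0.

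A late stop would also show in the data. Section E2.a starts women on "one tablet and 1 capsule (total of 2) of blinded study medication once a day". Take a woman at that level who stops on day 42. From Week 4 to Week 8 she should use 28 × 2 = 56 units; she uses 14 × 2 = 28, or 50%. At the escalated level of 4 units a day the figures are 56 of 112, again 50%. Over the whole period she has taken drug on 42 of 56 days, or 75%. The count alone cannot separate a stop from scattered missed doses, but the compliance assessment at the same visit can, and Section M has coordinators ask why doses were not taken.

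**The case for a change.** The best case for a change is that it would be cheap. A sentence defining early and one on summarising the counts would remove a choice that bears on a stated purpose of the pilot. Wide sampling error is no excuse for a removable one-directional error. The Operations Manual is not among the documents, so one cannot assume that it settles the matter.

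The day-28 arithmetic stands, and so does the observation that the word is undefined and the adherence summary unlisted. The harm does not stand, because it needs an analyst to borrow a rule from another section, for another term, against the ordinary sense of the word in SA 1. The obvious replacement definition gains little: counting any stop not resumed before the end of treatment, apart from isolated missed doses, leaves open whether a woman who skips her last two or three days has stopped early. As for the missing summary, doses taken over doses expected, by arm, is what any analyst would tabulate from counts the plan already collects.

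**Conclusion.** No change follows. The four-week rule cannot be met at an on-time Week 8 visit by a woman whose last dose is after day 28, but the plan does not use it to build the SA 1 count. On the plain reading the count misses nobody. On the strained reading it could miss at most about 2.3 to 6.4 of 10 stops. That range assumes a 20% stop rate in 50 women and a first-half to second-half hazard ratio between 3 and 0.5; none of these assumptions comes from the documents.

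The stakes are confined to a descriptive feasibility figure. The Week 8 comparisons under SA 2 to SA 5 do not use the rule, no go/no-go threshold for discontinuation is stated, and Section K ties the planning of a larger trial to the standard deviations and effect sizes. The measurements are little affected either: a woman who stops after Week 4 does not trigger the rule before Week 8, and the Week 8 and early-termination columns of E5 carry the same outcome tests. What remains is missing detail that analysts can supply from data already scheduled.
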